9 RANDOMIZATION PROCEDURE

Subject randomization will not be carried out in this study.

Approximately up to 32 subjects (up to approximately 16 subjects in Part A and 16 subjects in Part B) will be enrolled.

9.1 Blinding

The study is open label.

10 SAFETY ASSESSMENTS

GBT440 is not an approved drug and, as a result, the entire safety profile is not known at this time. This Phase 2 study will contribute to the understanding of the safety profile for GBT440 and for its use in IPF patients.

Safety assessments will consist of recording all AEs and SAEs, protocol-specified laboratory variables, vital signs, ECGs, and the results from other protocol-specified tests that are deemed critical to the safety evaluation of GBT440. Dedicated eCRFs will be used to collect information on specific AEs including SAEs, SUSARs, rashes and pregnancies.

10.1 Adverse Events (AE)

An AE is defined as any untoward medical occurrence in any subject enrolled in a clinical investigation administered a pharmaceutical product, -regardless of causal attribution.

An AE can be any unfavorable and/or unintended sign, symptom, or disease temporally associated with the use of an investigational product, whether or not it is thought to be related to the investigational product. In addition to new events, any increase in the severity or frequency of a pre-existing condition that occurs is considered an AE. This includes any side effect, injury, toxicity or sensitivity reaction.

Subjects will be monitored throughout the study for AEs, from the time informed consent is obtained until the last study visit (Day 120). Reporting of AEs prior to enrollment should only include SAEs or AEs resulting from any protocol-related interventions.

AEs that are identified at the last assessment visit as specified in the protocol must be recorded in the eCRF. All events that are ongoing at this time will be recorded as ongoing on the eCRF. All (both serious and non-serious) AEs must be followed until they are resolved or stabilized, or until reasonable attempts to determine resolution of the event are exhausted. The Investigator should use his/her discretion in ordering additional tests as necessary to monitor the resolution of such events.

All reported AEs will be coded using the current version of the Medical Dictionary for Regulatory Activities (MedDRA).

All procedures specified in [Section 10.3](#) are to be followed for reporting SAEs.

10.2 Recording Adverse Events

Adverse events are to be recorded on the AE page of the eCRF. The following information will be recorded at the time the AE is reported and during follow up during the course of the AE:

- Whether or not the AE is an SAE ([Section 10.2.2](#))
- AE severity using National Cancer Institute Common Terminology Criteria for Adverse Events, Version 4.03 (NCI CTCAE v4.03) ([Section 10.2.3](#))

- AE relationship to investigational product ([Section 10.2.4](#))
- Action taken, including but not limited to: none, study drug dose modification or discontinuation, required concomitant medication, required procedure, or other
- Outcome: recorded as event resolved, resolved with sequelae, ongoing, or death

10.2.1 *Assessment of Adverse Events*

The Investigator will assess each AE for seriousness, severity, and relationship to study drug.

10.2.2 *Serious Adverse Event (SAE)*

The Investigator is responsible for determining whether an AE meets the definition of an SAE. An SAE is any AE that results in any of the following outcomes:

- Death
- Life-threatening, i.e., an AE that places the subject at immediate risk of death
- Inpatient hospitalization or prolongation of existing hospitalization
- A persistent or significant disability or incapacity, i.e., a substantial disruption in the subject's ability to conduct normal life functions
- A congenital anomaly or birth defect in a neonate or infant born to a mother exposed to study drug
- Significant medical events that, in the opinion of the Investigator, may jeopardize the subject or may require medical or surgical intervention to prevent any of the outcomes listed in this definition.

SAEs will be reported to the Sponsor's designated CRO's Drug Safety Department within 24 hours of the Investigator, designee, or site personnel's knowledge of the event. Refer to "Reporting Serious Adverse Events" (details are provided in [Section 10.3.4](#)).

Note: Hospitalization is not considered to be an SAE if a subject has a hospitalization or procedure (e.g., elective surgery) during the study, that was scheduled prior to the subject entering the study (i.e., before the subject signed the informed consent) for a pre-existing condition (i.e., one that occurred before the study). However, if the event/condition worsens during the study, it must be reported as an AE (or SAE, if the event/ condition results in a serious outcome such as hospitalization).

10.2.3 *Protocol-Defined Events of Special Interest*

An adverse event of special interest (AESI) is any AE occurring from signing of the informed consent form (ICF) until the end of the study (Day 58) that results in:

- An allergic reaction/hypersensitivity Grade 2 or higher (as defined by NCI CTCAE v4.03)

AESIs will be reported to the CRO’s Drug Safety Department within 24 hours of the investigator, designee, or site personnel’s knowledge of the event.

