1.5.1 Safety Findings

To date, GBT440 has been well tolerated over a range of doses administered to healthy and SCD subjects, for up to 90 days.

As of 30 September 2016, a total of 259 subjects have received at least 1 dose of GBT440: 205 healthy subjects, 47 adult SCD subjects and 7 pediatric SCD subjects.

In Study GBT440-001, the majority of the adverse events (AEs) were mild or moderate (Grade 1 or Grade 2), most commonly headache or diarrhea, and no clinically significant findings in vital signs, 12-lead electrocardiograms (ECGs), or laboratory safety values were identified.

In the SCD subjects dosed for 90 days, the majority of the AEs were also mild or moderate (Grade 1 or Grade 2). The most common AEs, occurring in ≥ 2 subjects and at a similar frequency in GBT440 and placebo-treated subjects, were headache, back pain, fatigue, and rhinitis.

The AEs that occurred at a higher rate in subjects receiving GBT440 included cough, diarrhea, and rash, of which diarrhea and rash were considered treatment-related by the Investigator. No episodes of anaphylaxis, anaphylactoid, or hypersensitivity reactions were reported.

Rashes were morbilliform in nature, typically involved the trunk or extremities, associated with mild pruritus, resolving within 2 to 5 days (in one case with continued dosing), and were not associated with any systemic features.

Overall, 10 serious adverse events (SAEs) have been reported as of 30 September 2016, in 10 subjects with SCD, considered by the Investigator to be not related to the study drug. There were 7 events of sickle cell crisis (Grade 3), all occurring off treatment during follow-up (1 placebo; 6 GBT440); 1 event of presumed infection with hemolysis (Grade 2) (GBT440); 1 event of an ovarian cyst (Grade 3), occurring after the last dose of study drug (GBT440) and 1 event of Grade 2 upper respiratory tract infection requiring hospitalization (GBT440).

Please refer to the GBT440 IB for additional details on GBT440 safety findings.

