8 DOSAGE AND TREATMENT ADMINISTRATION

8.1 Treatment Regimen

GBT440 will be administered orally each day for 90 days. GBT440 will be administered as 300 mg capsules or tablets.

Part A:

- GBT440 900 mg: three 300 mg capsules or tablets

Part B:

- GBT440 1500 mg: five 300 mg capsules or tablets

Instructions for administration of study drug:

- Self-administered by subject in the morning
- May be taken with or without food
- May be taken with water or another non-alcoholic beverage
- Swallow the capsules or tablets whole

Subjects must be instructed not to take study drug on the day of their scheduled visits (refer to the Schedules of Assessments provided in Appendix A [[Table 15-1](#) for Part A; [Table 15-2](#) for Part B]).

Study drug will be administered at the site on these days, after completion of all the assessments scheduled for that visit. The subject should be instructed to swallow the capsules or tablets whole.

If a subject misses a dose of the study drug, they should resume normal dosing the next day; i.e., on the next day, the dose of study drug should be unchanged — not increased or decreased.

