If the clinically significant laboratory abnormality is not a sign of a disease or syndrome, the abnormality itself should be recorded as an AE or SAE on the eCRF. If the laboratory abnormality can be characterized by a precise clinical term, the clinical term should be recorded as the AE or SAE. For example, an elevated serum potassium level of 7.0 mEq/L should be recorded as "hyperkalemia."

Observations of the same clinically significant laboratory abnormality from visit to visit should not be repeatedly recorded as AEs or SAEs on the Adverse Event eCRF, unless their severity increases or decreases, or the seriousness or etiology changes.

10.3.5 *Reporting Serious Adverse Events (SAEs)*

All SAEs and AESIs, regardless of causal attribution, that occur in this study will be reported to the Sponsor's designated CRO's Drug Safety Department within 24 hours of the Investigator, designee, or site personnel's knowledge of the event. The SAE/AESI will be reported by completing the SAE/AESI eCRF in the EDC system.

In the event that the EDC system is not available, a paper SAE/AESI report form must be submitted to the CRO's Drug Safety Department ([contact] or faxed to [name]) within 24 hours of becoming aware of the event. The Principal Investigator or designee must complete the SAE/AESI eCRF page as soon as the EDC system becomes available.

Follow-up reports must be submitted in a timely fashion as additional information becomes available. The Sponsor or designee may request additional source documentation pertaining to the SAE/AESI from the investigational site. If a subject is permanently withdrawn from the study due to a SAE, this information must be included in the initial or follow-up SAE report in the eCRF.

The Investigator is responsible for notifying the Institutional Review Board (IRB) or Independent Ethics Committees (IEC) of SAEs, in accordance with local regulations. The Sponsor or designee is responsible for reporting SAEs to the relevant regulatory authorities, and participating Investigators, in accordance with ICH guidelines, FDA regulations, and/or local regulatory requirements.

Properly anonymized and de-identified documents (e.g., hospital discharge summaries, autopsy reports, and/or death certificates) as available will be provided to the CRO's Drug Safety Department for all reported SAEs/AESIs.

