- a. All screening evaluations must be completed and reviewed prior to Day 1 (Visit 2) to confirm the subject meets all eligibility criteria prior to dosing.
- b. All subjects who discontinue study or study drug prior to study completion and who are unwilling or unable to complete the remaining scheduled visits should return to the study site to complete all ET assessments (see [Section 6](#))
- c. Written informed consent must be obtained and documented prior to performing any study-specific screening procedure
- d. Demographics, medical history and baseline conditions obtained at screening should be reviewed again and any changes since screening noted in the eCRF
- e. After informed consent but prior to randomization only SAEs resulting from a protocol-mandated intervention should be reported. After randomization, all adverse events will be reported until study completion (Day 120).

- f. Includes evaluation of the head, eyes, ears, nose and throat and cardiovascular, respiratory, musculoskeletal, gastrointestinal, neurological, dermatologic systems. No rectal or pelvic examination is required. Record any observed abnormalities in the eCRF. At subsequent visits record new or worsened clinically significant findings on the eCRF.
- g. Perform a limited, symptom-directed examination as clinically indicated. Record new or worsened clinically significant findings in the eCRF.
- h. Includes heart rate, respiratory rate, systolic and diastolic blood pressure and temperature measured in a semi-recumbent or supine position and resting for at least 5 minutes.
- i. Performed at the time of Vital Signs assessment, with the subject breathing their supplemental O2 delivered at the usual prescribed rate and after the subject has rested for at least 5 minutes.
- j. Perform 12-lead ECG after the subject has been resting in a semi-recumbent or supine position for at least 5 minutes.
- k. Perform for all female subjects who are not post-menopausal or surgically sterile. On Day 1, urine pregnancy must be performed before any other assessments. The Investigator is to ensure that the result is negative prior to completing any other study related assessments and prior to administering investigational product to the subject.
- l. If a urine pregnancy test on Day 1 is positive, confirm the result with a serum pregnancy test. The serum pregnancy test must be available (and negative) prior to Day 1 dosing.

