- e After informed consent but prior to randomization only serious adverse events (SAEs) resulting from a protocol-mandated intervention should be reported. After randomization, all AEs will be reported until study completion (Day 120).
- f Includes evaluation of the head, eyes, ears, nose and throat and cardiovascular, respiratory, musculoskeletal, gastrointestinal, neurological, dermatologic systems. No rectal or pelvic examination is required. Record any observed abnormalities in the eCRF. At subsequent visits, record new or worsened clinically significant findings on the eCRF.
- g Perform a limited, symptom-directed examination as clinically indicated. Record new or worsened clinically significant findings in the eCRF.
- h Includes heart rate, respiratory rate, systolic and diastolic blood pressure and temperature measured in a semi-recumbent or supine position and resting for at least 5 minutes.
- i Performed at the time of Vital Signs assessment, with the subject breathing their supplemental O₂ delivered at the usual prescribed rate and after the subject has rested for at least 5 minutes. On Screening and Day 1 visits must be performed prior to other assessments to ensure eligibility.
- j Perform 12-lead ECG after the subject has been resting in a semi-recumbent or supine position for at least 5 minutes.
- k Perform for all female subjects who are not post-menopausal or surgically sterile. On Day 1, urine pregnancy must be performed before any other assessments. The Investigator is to ensure that the result is negative prior to completing any other study related assessments and prior to administering investigational product to the subject.
- l If a urine pregnancy test on Day 1 is positive, confirm the result with a serum pregnancy test. The serum pregnancy test must be available (and negative) prior to Day 1 dosing.
- m Instructions for per protocol performance of the oxygen titration, 6-minute walk (and Borg Dyspnea Scale) and ABG tests are provided in the procedure manual.
- n The ATAQ, SGRQ and End of Treatment questionnaires should be self-administered by the subject using the paper forms provided by the Sponsor prior to all other non-PRO assessments and before the subject receives any disease-status information during that assessment. The End of Treatment questionnaire is to be administered at the Day 120 visit, if it was not administered at the Day 90 visit.

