#### **8.4.3 Adverse Events**

Each reported AE term will be mapped to PT and SOC using the MedDRA Version 20.

Treatment-emergent adverse events (TEAEs) are defined as any event that occurs or worsens on or after the first dose of study drug and within 30 days after the last dose. Treatment-emergent adverse events (TEAEs) will be summarized based on the number (%) of subjects experiencing events by SOC and PT. The denominator for the percentage will be based on the number of subjects in the Safety population (i.e., those that received at least one dose of study drug).

A subject reporting the same AE more than once will be counted only once when calculating incidence 1) within a given system organ class, and 2) within a given system organ class and preferred term combination. For such cases, the maximum CTCAE toxicity grade and strongest causal relationship to study treatment for the event will be used in the incidence calculations.

An overall summary will be presented that includes the number of TEAEs and the number and percentage of subjects who experienced at least one TEAE. This summary will also include TEAEs  $\geq$  Grade 3, TEAEs possibly/probably related to study drug, serious adverse events (SAEs), TEAEs leading to discontinuation of study drug, and deaths.

Summaries of the following TEAEs will be provided by SOC and PT:

- All TEAEs
- Treatment-related AEs
- TEAEs by maximum severity, table includes a summary of AEs grade 3 or higher
- Serious TEAEs (AE listing)
- TEAEs that led to dose modification or permanent discontinuation of GBT 440 (listing only )

Summaries presented by SOC and PT will be ordered alphabetically for SOC and descending frequency within SOC of PT based on the total GBT 440 group.

All AE data will be summarized for each dose level (900 mg, 1500mg).

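### The AESI definition closes at Day 58, although each subject's study ends at Day 120. Taken literally, it removes the 24-hour reporting duty for non-serious Grade 2+ hypersensitivity on Days 59 to 120.

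*Protocol*

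**What the plan says.** Protocol Section 10.2.3 sets the AESI window from signing of the consent form "until the end of the study (Day 58) that results in" an allergic or hypersensitivity reaction of Grade 2 or higher by CTCAE v4.03. The reaction need not be serious. Sites must report an AESI to the CRO's drug safety department within 24 hours of learning of it.

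Elsewhere the protocol gives a different end for each subject:

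- Section 8.1: "GBT440 will be administered orally each day for 90 days".
- Section 3.1: a 90-day treatment period, then 30 days of safety follow-up.
- Section 10.1: adverse events are monitored "from the time informed consent is obtained until the last study visit (Day 120").
- Appendix A, Table 15-1, footnote e: "After randomization, all adverse events will be reported until study completion (Day 120"). Table 15-2, footnote e: "After randomization, all AEs will be reported until study completion (Day 120"). Both tables label the Day 120 column as end of study.

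Section 10.3.5 states the general expedited rule: "All SAEs and AESIs, regardless of causal attribution, that occur in this study will be reported" within 24 hours. It gives no start or end day for AESIs.

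On the analysis side, SAP Section 8.4.3 defines a treatment-emergent event as "any event that occurs or worsens on or after the first dose of study drug and within 30 days after the last dose". Neither that section nor protocol Section 11.3.2 plans a separate AESI summary.

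**The concern.** The day sits inside the definition that triggers a 24-hour duty. A site that follows the words reports AESIs to Day 120. A site that follows the number stops at Day 58, while the subject still has about a month of dosing to come. Both could say they complied with Section 10.2.3, so the same event could be expedited at one site and entered only as an ordinary adverse event at another.

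The uncovered period matters because the protocol reports little prior safety experience for part of it. Section 1.5.1 says of the sickle cell subjects dosed for 90 days: "No episodes of anaphylaxis, anaphylactoid, or hypersensitivity reactions were reported". By Section 1.5, those subjects received 700 or 900 mg. The earlier IPF study doses for 28 days, and the protocol reports no 90-day findings at 1500 mg. Section 1.5.1 also reports rash at a higher rate on study drug, considered treatment-related.

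**Working it through.** **Step 1. Can Day 58 be reproduced?**

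- Treatment plus follow-up (Section 3.1): 90 + 30 = 120. This agrees with Section 10.1, both footnotes e, both end-of-study columns, and the roughly 120 days from first dose to last visit in Section 5.3.
- With the ±5-day window on the final visit: Day 115 to Day 125.
- Trial-level definition (Section 3.1): the last subject's last visit, about 120 days after the last enrolment.
- Scheduled visits: the nearest is Day 60 ±5. None is set at Day 58.

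None of these gives 58. One possible origin is the earlier 28-day IPF study, since 28 + 30 = 58, but the documents do not give that study's follow-up length, so this is conjecture.

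**Step 2. What a literal Day 58 leaves out** (nominal schedule, counted from Day 1)

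- Dosing days after Day 58: 90 − 58 = 32, and 32/90 = 36%.
- Follow-up days: 120 − 90 = 30.
- Total: 120 − 58 = 62 days, and 62/120 = 52%.

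With visit windows:

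- Last visit on Day 115 to 125: 115 − 58 = 57 to 125 − 58 = 67 study days.
- If the last dose moves with the Day 90 ±5 visit, where drug is given on site: 85 − 58 = 27 to 95 − 58 = 37 dosing days. This is an assumption, because Section 8.1 fixes dosing at 90 days and SAP Section 5 allows up to 90.

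**Step 3. Scheduled adverse-event reviews after Day 1**

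- Part A: Days 15, 30, 45, 60, 90, 120. Nominally 3 of 6 fall after Day 58.
- Part B: Days 15, 30, 60, 90, 105, 120. Nominally 4 of 6 fall after Day 58.
- The Day 60 visit may be held as early as Day 55. If it falls by Day 58, the counts are 2 of 6 and 3 of 6.

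**Step 4. Does another 24-hour rule cover the gap?**

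- Sections 10.2.2 and 10.3.3: serious events, or events that become serious.
- Section 10.5: pregnancies.
- Section 10.3.5: SAEs and AESIs, with AESI as defined in Section 10.2.3.

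A Grade 2+ hypersensitivity reaction on Days 59 to 120 that is not serious meets none of these if Day 58 is taken literally.

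**Step 5. Is any analysis affected?**

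The SAP's treatment-emergent window runs to 30 days after the last dose, nominally 90 + 30 = Day 120. It does not use the AESI window, and no AESI table is planned. No summary changes.

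**The case against.** The strongest reply is that this is a slip with little practical effect. The words before the bracket refer to the end of the study, Day 120 carries that label in both schedules, and there is no Day 58 visit at which a site would stop. Section 10.3.5 speaks of AESIs that occur in the study, which favours the Day 120 reading.

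The protocol also has other routes by which the sponsor would hear of a reaction:

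- Serious hypersensitivity and Grade 3 or higher rash require study drug to be stopped (Section 6.3).
- Stopping for an adverse event requires notice to the sponsor's medical director and the CRO medical monitor (Section 10.4).
- Dose changes and interruptions involve the medical director (Sections 8.3 and 8.3.2).
- Rashes have a dedicated case report form (Section 10).
- An investigator may judge a reaction a significant medical event and so an SAE (Section 10.2.2).

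Much of this stands. These routes narrow the gap mainly to non-serious Grade 2+ reactions with no change in dosing. They do not close it: apart from the SAE route, none has a 24-hour limit. Whether any site would stop at Day 58 cannot be known, so the consequence remains conditional on a literal reading.

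Two further points are fair. The 52% is calendar time, not risk, because the documents give no onset times. And the absence of hypersensitivity reactions in the sickle cell subjects does not supply a rate for IPF patients, so no event count is estimated here.

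The start of the window has a conflict of its own. Section 10.2.3 begins at consent, while Section 10.3 and footnote e limit reporting before dosing or randomization to SAEs from protocol interventions. That is a separate matter and does not bear on the end date.

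**Conclusion.** The point holds. Day 58 is an error in current, operative protocol text, and every other statement of a subject's end of study gives Day 120. Applied literally, it takes 62 of 120 study days (52%), including 32 of 90 dosing days (36%), out of the AESI window. Non-serious Grade 2+ hypersensitivity in that period would then have no 24-hour reporting duty.

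These figures rest on the nominal schedule; visit windows move the total to between 57 and 67 days. The finding concerns consistent expedited reporting of the protocol's only AESI. It does not involve lost data or a biased analysis: adverse events are collected to Day 120, serious events keep their 24-hour clock, and the SAP summaries are unaffected. It should be fixed, at modest priority.

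**What to change.** In Section 10.2.3, end the AESI window at the last study visit (Day 120), in line with Section 10.1 and footnote e of Tables 15-1 and 15-2. Naming the last study visit is better than keeping the present words without the number, because Section 3.1 defines the end of the study at trial level as the last subject's last visit. It also covers a subject whose last visit is Early Termination. Make the same correction in any safety-reporting instructions given to sites.

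The cost is one phrase in the protocol and a check of those instructions. It adds no visits or assessments and changes no dose, stopping rule or planned analysis. Any added work is the expedited reporting of whatever qualifying events occur after Day 58.
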